## LIST OF ABBREVIATIONS

Abbreviation	Definition
ACE	Angiotensin converting enzyme
ACEi	Angiotensin converting enzyme inhibitors
ADA	Anti-drug antibodies
ADL	Activities of daily living
AE	Adverse event
ALT	Alanine aminotransferase
ALP	Alkaline Phosphate
aPTT	Activated partial thromboplastin time
ARB	Angiotensin Receptor Blockers
AST	Aspartate aminotransferase
BMI	Body mass index
CBER	Center for Biologics Evaluation and Research
CRP	C-reactive protein
CTCAE	Common Terminology Criteria for Adverse Events
DMP	Data management plan
EC	Ethics Committee
ECG	Electrocardiogram
eCRF	Electronic case report form
EDC	Electronic data capture
ER	Emergency room
GCP	Good Clinical Practice
HbA1c	Glycosylated hemoglobin
HBsAg	Hepatitis B surface antigen
HCV	Hepatitis C virus
HIV	Human immunodeficiency virus
HR	Heart rate
ICF	Informed Consent Form
ICH	International Conference on Harmonisation
INR	International normalized ratio
IV	Intravenous
IWRS	Interactive Web Response System
KLK1	Kallikrein-1
LAR	Legally authorized representative
LDH	Lactate dehydrogenase

Abbreviation	Definition
LLOQ	Lower limit of quantitation
MAD	Multiple ascending dose
MAP	Mean arterial blood pressure
MCH	Mean corpuscular hemoglobin
MCHC	Mean corpuscular hemoglobin concentration
MCV	Mean corpuscular volume
MedDRA	Medical dictionary for regulatory activities
MMP-9	Matrix metalloproteinase - 9
NIH	National Institutes of Health
NIHSS	National Institutes of Health Stroke Scale/Score
NOAEL	No observable adverse effect level
PBS	Phosphate buffered saline
PD	Pharmacodynamic(s)
PK	Pharmacokinetic(s)
PNAU	P-nitroaniline unit
PT	Prothrombin time
rhKLK1	Recombinant human kallikrein-1
SAD	Single ascending dose
SAE	Serious adverse event
SAP	Statistical analysis plan
SC	Subcutaneous
SOP	Standard operating procedure
TEAE	Treatment-emergent adverse event
tPA	Tissue plasminogen activator
VEGF	Vascular epithelial growth factor

**PROTOCOL SYNOPSIS**

PROTOCOL NUMBER	DM199-2017-001
PROTOCOL TITLE	A Randomized, Double-blind, Placebo-controlled Phase II Multi-Center Investigation to Assess the Safety and Tolerability of DM199 Administered Intravenously and Subcutaneously in Subjects with Acute Ischemic Stroke
STUDY PHASE	II
INVESTIGATIONAL PRODUCT (IP)	DM199
SPONSOR	DiaMedica Australia Pty Ltd [name] [name], Australia
NATIONAL PRINCIPAL INVESTIGATOR	[name] Royal Melbourne Hospital [name] [name], Australia
RESPONSIBLE CRO	Novotech [name] [name], Australia
CENTRAL LABORATORY	Sonic Clinical Trials [name] [name], Australia
STUDY RATIONALE	
DM199 is a recombinant human version of the KLK1 protein. In China, a urinary-derived form of this protein (Kailikang®) is approved as a treatment for acute ischemic stroke based on at least one large randomized, double-blind, placebo-controlled trial. The primary mechanism of KLK1 treatment appears to be an improvement of blood flow in capillaries and formation of new capillaries over the longer term. DM199 has been shown to be safe and well-tolerated in multiple Phase I and Phase IIA clinical trials. Moreover, these trials have demonstrated that DM199 can be dosed to achieve plasma exposures similar to those of Kailikang®.
 
DiaMedica Therapeutics Inc. is conducting this Phase II study in patients with acute ischemic stroke to establish safety and tolerability in this patient population. This study will also explore the effect of treatment on standard efficacy endpoints and biomarkers measured at various time points after the stroke. IV and subcutaneous routes of administration will be tested.

STUDY DESIGN	This is a randomized, double-blind, placebo-controlled Phase II, multi-center study of DM199. Subjects presenting with acute ischemic stroke will be randomized 1:1 to placebo or DM199

	administered by a single intravenous (IV) dose followed by subsequent subcutaneous (SC) doses.
OBJECTIVE	The objective of this study is to evaluate the safety and tolerability of DM199 in treating subjects presenting with acute ischemic stroke.
PRIMARY ENDPOINTS	
 
1. Safety as assessed by: 
 
• Incidence, severity and causality of adverse events (AEs) and serious adverse events (SAEs)
 
• Physical examination changes from baseline (days 4, 22, 56, and 90)
 
• Vital sign changes from baseline (resting heart rate, systolic/diastolic blood pressure, respiratory rate, and temperature) (days 1, 4, 7, 10, 13, 16, 19, 22, 56, and 90)
 
• Hematology and chemistry parameter changes from baseline (days 4, 22, 56, and 90)
 
• 12 lead ECG changes from baseline (days 1, 4, and 22)
 
 
 
2. Tolerability as assessed by incidence and severity of injection site adverse events
 

SECONDARY ENDPOINTS	
 
1. Efficacy as assessed by: 
 
• NIH Stroke Scale (days 22 and 90)
 
• Barthel Index (days 22 and 90)
 
• Modified Rankin Scale (days 22 and 90)
 
 
 
2. Plasma concentration of DM199 (days 2, 22, and 90)
 
3. Pharmacodynamics as assessed by: 
 
• Plasma C-reactive protein (CRP) (days 2, 22, and 90)
 
• Plasma MMP-9 (days 2, 22, and 90)
 
• Plasma VEGF (days 2, 22, and 90)
 
• Plasma DM199 ADA (days 2, 22, and 90)
 
 
 

EXPLORATORY ENDPOINTS	
 
1. Urinary KLK1 concentration (days 4, 13, 22, and 90)
 
2. Pharmacodynamics as assessed by: 
 
• Plasma tPA (days 2, 22, and 90)
 
• Plasma Nitric Oxide as NOx (days 2, 22, and 90)
 
• Plasma Prostaglandins (E2) (days 2, 22, 90)
 
 
 

SAMPLE SIZE & SAMPLE SIZE DETERMINATION	No formal sample size estimation was performed. Up to 66 subjects will be enrolled to achieve approximately 60 completed subjects, based on an estimated drop-out rate of 10%. Subjects will be randomized 1:1 to receive DM199 or placebo, resulting in 33 enrolled subjects per treatment group. A sample size of 30 completed subjects in each treatment group is considered adequate to evaluate the safety and tolerability of DM199.
INCLUSION CRITERIA	
 
1. Subject is <math>\geq 18</math> years of age.
 
2. Subject has been diagnosed with acute ischemic stroke with onset <math>\leq 24</math> hours from enrollment.
 
3. Subject has NIH stroke score (NIHSS) <math>\geq 6</math> and <math>\leq 25</math>.  NOTE: For subjects who have received treatment with either tPA (or similar) or any type of mechanical intervention the assessment of the NIHSS must occur at least 1 hour after such treatment for purposes of evaluating eligibility for this study.
 
4. Subject or legally authorized representative is willing and able to sign written informed consent.
 

EXCLUSION CRITERIA	
 
1. Subject is currently prescribed angiotensin-converting-enzyme inhibitors (ACEi) and is unable or unwilling to convert to another antihypertensive pharmacological treatment for the duration of the study.
 
2. Subject has a history of significant allergic diathesis such as urticaria, angioedema or anaphylaxis.
 
3. Subjects with current malignancy or active malignancy <math>\leq 5</math> years prior to enrollment except basal cell or squamous cell carcinoma of the skin or in situ cervical cancer that has undergone potentially curative therapy and at least six months have elapsed since the procedure.
 
4. Subject has a history of clinically significant acute bacterial, viral, or fungal systemic infections in the last four weeks prior to enrollment.
 
5. Subject has clinical or laboratory evidence of an active infection at the time of enrollment.
 
6. Subject has known alpha 1-antitrypsin deficiency (<math>\alpha 1</math>-antitrypsin deficiency).
 
7. Subject has a known diagnosis of human immunodeficiency virus (HIV), hepatitis B surface antigen (HBsAg), or anti-hepatitis C virus (Anti-HCV) at screening.
 

	
8. Subject is pregnant or nursing.
 
9. Subject is male or female of childbearing potential, is participating in heterosexual sexual activity that could lead to pregnancy, and is unable or unwilling to practice medically effective contraception during the study.
 
NOTE: Subjects should agree to use two reliable methods of contraception (e.g., double-barrier condom plus diaphragm, condom or diaphragm plus a stable dose of hormonal contraception) throughout the study period and until three months after receiving study treatment.
 
NOTE: A negative urine pregnancy test will be documented during screening.
 
10. Subject is participating in any other drug study <math>\leq</math> 4 weeks or 5 half-lives of the investigational product, whichever is longer.
 
11. Subject does not have sufficient venous access for infusion of study treatment or blood sampling.
 
12. In the opinion of the Investigator, subject is unlikely to be followed for the duration of the study.
 
13. Subject is unable or unwilling to comply with protocol requirements, including assessments, tests, and follow-up visits.
 
14. Subject has any other medical condition which in the opinion of the Investigator will make participation medically unsafe or interfere with the study results.

--	--

# 1 INTRODUCTION

## 1.1 BACKGROUND

Acute ischemic stroke is a debilitating disease that is a major medical and economic concern among nations whose demographics include an aging general population. At present, the only pharmacological treatment for stroke is tissue plasminogen activator (tPA) which must be given within 4.5 hours of the ischemic event, where it has been shown to significantly improve function vs placebo in many patients (Cheng & Kim, 2015). Unfortunately, there are currently no medical therapies available to provide further functional improvement beyond tPA, for use after the 4.5-hour window when tPA cannot be administered.

Kallikrein (specifically, tissue kallikrein known as KLK1) is an endogenous enzyme that produces kinins and is the most potent natural vasodilative mechanism known acting through the Bradykinin 1 and 2 receptors. The kinins, including Bradykinin (BK), are rapidly degraded in the blood by ubiquitous peptidases, most notably angiotensin converting enzyme (ACE). Indeed, many of the benefits ascribed to ACE inhibitors (ACEi) appear to involve increases in BK levels.

KLK1 has been shown to protect against ischemic brain injury through multiple signalling pathways including anti-inflammation, anti-apoptotic effect, promoting angiogenesis and neurogenesis, and improved cerebral blood flow through vasodilation. In addition to ischemic brain injury, research on hind limb ischemia, cardiac infarction, and renal ischemia further indicates that kallikrein may be a novel angiogenic protein. For stroke patients, improving cerebrovascular perfusion, dilation of the arteriole, decreasing inflammation, and formation of new vessels in the penumbra region remains a good option to help rescue injured tissue and alleviate neurologic deficits. KLK1 appears to endow these properties.

DiaMedica Therapeutics Inc. (DiaMedica) has developed a recombinant form of KLK1 (rKLK1, DM199) and has previously completed single ascending dose (SAD) and multiple ascending dose (MAD) trials of the subcutaneous dose form. In addition, a small pilot trial in patients with mild type 2 diabetes was conducted over 28 days. To date, DM199 has been administered to 104 healthy volunteers and patients. In all the trials, DM199 proved to be safe and well tolerated. At very high doses (0.3-0.5 mg/kg), hypotension was observed which was expected and consistent with the mechanism of action. No anti-drug antibodies were observed at 28 days.

## 1.2 NONCLINICAL SUMMARY

The pharmacokinetics (PK) of DM199 was characterized in male and female cynomolgus monkeys (2 males and 2 females) following subcutaneous (SC) injection at 1.80 mg/kg/day for 14 days. The  $C_{max}$  of DM199 was reached at 2 hours post-dose for the females and generally by 4 hours for the males on Days 2 and 14. A decrease was observed in the mean exposure parameters with accumulation ratios ranging from 0.198 to 0.380-fold. The terminal elimination phase could not be characterized for any of the profiles. No consistent gender differences in systemic exposure were observed. The PK of DM199 in plasma was also characterized in male Sprague-

Dawley rats when delivered by a single dose intravenously (IV) and SC at dose levels of 0.01049 and 0.1049 mg/kg. For 0.1049 mg/kg by SC administration, peak DM199 mean plasma concentration was observed at 12 hours followed by a shallow mono-exponential decline where the terminal elimination phase was not reached. For IV administration,  $t_{max}$  was observed at 15 minutes for 0.01049 mg/kg and 5 minutes for 0.1049 mg/kg. Limited exposure did not allow for characterization of the terminal phase at 0.01049 mg/kg by IV administration. For 0.1049 mg/kg by IV administration, the peak DM199 plasma concentration was followed by a mono-exponential decline and  $t_{1/2}$  was estimated to be 6.44 hours. Absolute bioavailability using  $C_{max}$  (SC/IV) was 53% for the 0.1049 mg/kg dose level.

There were no observed toxicity effects of DM199 in Sprague-Dawley rats when given by SC injection once during an escalating dose at a dose level up to 3.69 mg/kg. In exploratory non-GLP single dose escalation study in cynomolgus monkeys, DM199-related findings were limited to a decrease in mean arterial blood pressure (MAP) at the high dose (3.6 mg/kg) compared to the control dose. Due to the magnitude of the drop in MAP, the 3.6 mg/kg dose was considered to be the observed adverse effect dose.

In repeated dosing studies, administration of DM199 by SC injection at dose levels of 1.44, 2.88 and 3.6 mg/kg/day for 28 days was well tolerated in rats. There were no DM199 associated findings for clinical observations, body weights, food consumption, ophthalmic observations, hematology, clinical chemistry, coagulation, urinalysis, gross pathology observations, or organ weights and ratios. Administration of DM199 by SC injection for 1 month was well tolerated in cynomolgus monkeys at all dose levels. A single high dose female animal was euthanized for humane reasons on Day 8 for telemetry implant-related complications that were not due to test article administration. DM199-related findings were limited to a non-dose-related microscopic finding at the injection site at all dose levels and an increase in liver-specific enzyme serum levels at 1.44 mg/kg/day. Based on these results, the no observable adverse effect level (NOAEL) was considered to be 1.44 mg/kg/day.

Treatment with DM199 in rodent models of type 2 diabetes mellitus restored insulin sensitivity and improved insulin secretion. Treatment of non-obese diabetic mice attenuated the development of autoimmune reaction that results in type 1 diabetes mellitus. At 7 weeks of treatment, the non-obese diabetic mice developed a 6-fold increase in circulating C-peptide without a detectable increase in insulin, episodes of hypoglycemia or increase in beta cell mass.

### 1.3 CLINICAL SUMMARY

The same formulation of DM199 has been tested in Phase I and Phase II clinical studies. A single ascending dose study was conducted to assess the safety and pharmacokinetics of DM199 in healthy volunteers. This was a double-blind placebo-controlled trial including a total of 18 volunteers between the ages of 20 and 64. DM199 was tested at doses of 1.5, 5, 15, 30 and 50  $\mu$ g/kg administered subcutaneously. These doses were generally safe and well-tolerated. Drug-

related side effects were observed after the 50 µg/kg dose and were associated with postural hypotension.

A multiple ascending dose study was conducted in healthy volunteers to assess the pharmacokinetics, safety and tolerability of DM199 after chronic dosing once every 3 days for 16 days (6 doses total). The study included 18 volunteers between the ages of 21 and 64, who received ascending doses of 3, 15 and 25 µg/kg over the course of the study by subcutaneous injection. DM199 was safe and well-tolerated at all doses.

DM199 was tested in a Phase II study involving 37 patients with Type 2 Diabetes. Patients were treated with either placebo, 15 and 30 µg/kg DM199 administered subcutaneously for 28 days. The primary endpoint of blood glucose concentration was not different between groups treated with placebo or either dose of DM199. There were 15 adverse events that were considered related to study treatment. All were deemed mild to moderate (Grade 1-2) in severity. These included two cases of hypoglycemia, one observation of postural hypotension, two observations of a mild headache and eight reports of injection site irritation. There was a single severe adverse event (seizure) that was considered to be not related to study treatment.

An open label, Phase IB, single center, ascending dose study was completed to assess the safety and tolerability of DM199. The purpose of the study was to characterize the pharmacokinetics and pharmacodynamics after IV and SC dosing in healthy subjects. A total of 36 subjects were enrolled. The initial component of this study was a single ascending study focusing on a 30-minute infusion of DM199 at doses of 0.25, 0.5, 0.75 and 1 µg/kg. All doses were considered to be safe and well-tolerated. The pharmacokinetic profile of 0.75 µg/kg most closely matched that of urinary KLK1 (Kailikang®), a product that is currently marketed in the People's Republic of China for treating acute ischemic stroke. The second component of the study directly compared an IV infusion of 0.75 µg/kg DM199 to a 3 µg/kg subcutaneous injection. Both approaches generated similar peak plasma concentrations, but the DM199 plasma exposure was substantially longer after subcutaneous injection compared to IV administration. These doses were considered safe and well-tolerated with very few reported adverse events. The dosing strategy for this study is founded on these pharmacokinetic results and is designed to rapidly generate presumed therapeutic concentrations of DM199 and maintain that concentration for the subsequent 22 days of treatment.

[figure not shown]
## 1.4 RATIONALE

DM199 is being developed as a new biological treatment for acute ischemic stroke. The purpose of this Phase II study is to assess safety and tolerability of DM199 in patients with acute ischemic stroke.

## 2 STUDY DESIGN

This is a randomized, double-blind, placebo-controlled Phase II, multi-center study of DM199. Subjects presenting with acute ischemic stroke will be randomized 1:1 to placebo or DM199

administered by a single intravenous (IV) dose followed by subsequent subcutaneous (SC) doses. Figure 1 depicts the overall study design.

**Figure 1. Schematic Study Design**

## 2.1 OBJECTIVE

The objective of this study is to evaluate the safety and tolerability of DM199 in treating subjects presenting with acute ischemic stroke.

## 2.2 ENDPOINTS

### 2.2.1 Primary Endpoints

The primary endpoint of this study is to evaluate the safety and tolerability of DM199. Endpoints will be assessed as follows:

1. Safety:
  - Incidence, severity and causality of adverse events (AE) and serious adverse events (SAEs)
  - Physical examination changes from baseline (days 4, 22, 56, and 90)
  - Vital sign changes from baseline (resting heart rate, systolic/diastolic blood pressure, respiratory rate, and temperature) (days 1, 4, 7, 10, 13, 16, 19, 22, 56, and 90)
  - Hematology and chemistry parameter changes from baseline (days 4, 22, 56, and 90)
  - 12 lead ECG changes from baseline (days 1, 4, and 22)
2. Tolerability as assessed by incidence and severity of injection site adverse events.

### **2.2.2 Secondary Endpoints**

The secondary endpoints of this study are to evaluate:

1. Efficacy as assessed by:
  - NIH Stroke Scale (days 22 and 90)
  - Barthel Index (days 22 and 90)
  - Modified Rankin Scale (days 22 and 90)
2. Plasma concentration of DM199 (days 2, 22, and 90)
3. Pharmacodynamics as assessed by:
  - Plasma C-reactive protein (CRP) (days 2, 22, and 90)
  - Plasma MMP-9 (days 2, 22, and 90)
  - Plasma VEGF (days 2, 22, and 90)
  - Plasma DM199 ADA (days 2, 22, and 90)

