3. Vital sign measurements include heart rate, systolic and diastolic blood pressure, respiratory rate, and body temperature. All measurements to be collected at baseline, on all dosing days 30 minutes post IV dose and 2 ± 0.25 hours post SC dose on days 1 and 4, post dose on days 7, 10, 13, 16, 19 and 22, and Days 56 and 90. Measurements will be captured after resting in a seated position for five minutes.
4. 12-lead ECG to occur at baseline, and post-dose on days 1, 4 and 22.
5. Completed at site for women of child bearing potential only.
6. Urine collection for testing of urinary KLK1 concentration to be obtained at baseline (anytime prior to first dose of study treatment), and pre-dose on days 4, 13, 22 and 90.

7. Clinical laboratory tests include clinical chemistry, hematology, urinalysis, and coagulation. Samples collected pre-dose at baseline and days 4, 22, 56, and 90. Day 1 samples collected post-IV dose but pre-SC dose.
8. DM199 labs include plasma concentration of DM199 and PD biomarkers at baseline and days 2, 22, and 90. Samples collected pre-dose.
9. Single 40 minute IV infusion of study treatment with DM199 or placebo to occur on day 1; subcutaneous (SC) dose between 2 and 12 hours after start of infusion, then every 72 ( $\pm$  2) hours after the first SC dose for the remainder of the 22-day treatment period, for a total of eight SC doses.
10. For subjects undergoing reperfusion treatment prior to study enrollment, the NIHSS must occur at least 1 hour after treatment completion.
11. Adverse event (AE) collection will occur from time of consent to subject withdrawal. AEs will be captured during all hospitalizations and study visits or between visits as reported by the subject.
12. For any early subject withdrawal, every effort should be made to complete an early withdrawal visit. Assessments marked as (X) are only required if withdrawal occurs during the treatment period (day 1-22).

[figure not shown]

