### 5.9 CENTRAL LABORATORY ASSESSMENTS

#### 5.9.1 Clinical Laboratory

Pre-dose sample collection for Chemistry, Hematology, Urinalysis, and Coagulation will be collected, stored, and shipped according to the Central Laboratory Manual at baseline and days 4, 22, 56, and 90. Day 1 samples will be collected post-IV dose, but pre-SC dose. Urine pregnancy test is to be confirmed at the site (refer to **5.8 Urine Pregnancy Test**). **Table 2** describes the parameters to be measured.

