### 5.9.2 DM199 Laboratory

Pre-dose sample collection for plasma concentration of DM199 and pharmacodynamic biomarkers will be collected, stored, and shipped according to the Central Laboratory Manual at baseline and on days 2, 22, and 90. Urinary KLK1 concentration will be collected, stored, and shipped according to the Central Laboratory Manual at baseline and days 4, 13, 22 and 90.

**Table 3** describes the parameters to be measured.

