**Table 3: DM199 Laboratory Collection Parameters**

Analysis	Parameters
Pharmacokinetic biomarkers	Plasma concentration of DM199
Diagnostic biomarkers	Urinary concentration of KLK1
Pharmacodynamic biomarkers	CRP, MMP-9, VEGF, Nitric Oxide [NOx], Prostaglandins [E2], DM199 ADA, and tPA

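### In subjects who complete the study, an anti-drug antibody response that appears after the Day 22 draw and clears before Day 90 would go undetected, although blood is already drawn at Day 56

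*Combined protocol and SAP*

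**What the plan says.** Section 2.2.2 lists ADA under pharmacodynamics as "Plasma DM199 ADA (days 2, 22, and 90"; the synopsis and Section 8.2.2 give the same days. Table 3 places it in the PD panel: "CRP, MMP-9, VEGF, Nitric Oxide [NOx], Prostaglandins [E2], DM199 ADA, and tPA". It therefore follows that panel's schedule. Table 1, footnote 8 states "DM199 labs include plasma concentration of DM199 and PD biomarkers at baseline and days 2, 22, and 90", taken pre-dose, and Section 5.9.2 repeats "at baseline and on days 2, 22, and 90". These places agree with one another.

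Clinical laboratory blood follows a different schedule. For chemistry, hematology and the remaining tests, Section 5.9.1 reads "Urinalysis, and Coagulation will be collected, stored, and shipped according to the Central Laboratory Manual at baseline and days 4, 22, 56, and 90". Table 1 confirms a clinical laboratory draw at Day 56 and none for the DM199 panel.

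The only earlier immunogenicity result is in Section 1.1: "No anti-drug antibodies were observed at 28 days".

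**The concern.** An antibody to an administered protein develops on its own time course, and that course need not match that of CRP, MMP-9 or VEGF. The protocol gives no ADA-specific reason for the days chosen. They appear to have come with the PD panel.

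Two consequences follow. The Day 2 sample is spent about a day after first exposure, when little beyond the baseline status can be expected. And because the Day 22 sample is taken before that day's injection, no scheduled sample covers the weeks just after the full course of one infusion and eight injections. ADA is the trial's only direct measure of immunogenicity, in a study whose objective is safety and tolerability. If no subject tests positive, the report could not distinguish no response from a response that came and went between Day 22 and Day 90.

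**Working it through.** **Inputs**
- ADA days: baseline, 2, 22 (pre-dose), 90 (Sections 2.2.2, 8.2.2 and 5.9.2; Table 1, footnote 8).
- Treatment 22 days, follow-up 68 days (Section 2.4).
- Visit windows: Day 56 ± 2 days and Day 90 ± 2 days (Table 1).
- Eight SC doses, 72 hours apart (Section 4.1).
- Up to 66 enrolled for about 60 completers, 30 per group (Section 2.3).
- ADA onset time, duration and rate: not given anywhere.

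**1. The plan's own figure.** 90 − 22 = 68 days, which matches the follow-up in Section 2.4. With the Day 90 window: 88 − 22 = 66 and 92 − 22 = 70.

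**2. Where the samples fall.** Day 2 is 2 − 1 = 1 day after first exposure, and Day 22 is 22 − 1 = 21 days after. The eighth SC dose comes 7 × 72 = 504 hours (21 days) after the first, so the pre-dose Day 22 sample precedes it.

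**3. What is detected.** A response with onset on day *o* lasting *d* days is seen if some sample day *s* satisfies *o* ≤ *s* ≤ *o* + *d*. After Day 22, a completer's response is missed when *o* > 22 and *o* + *d* < 90. It is seen if it is present on Day 22 or still present on Day 90. (A response that both formed and cleared between Day 2 and Day 22 would also be missed. The point does not rest on that 20-day interval, and the change below does not address it.)

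**4. With ADA moved from Day 2 to Day 56.** The follow-up gaps become 56 − 22 = 34 and 90 − 56 = 34 days. With windows, the longest possible are 58 − 22 = 36 and 92 − 54 = 38. Samples per subject: four now (baseline, 2, 22, 90) and four after (baseline, 22, 56, 90).

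**5. Why no share missed is claimed.** Assume that onset is uniform over a window, that duration is fixed, and that any response present on a sample day is detected. The share missed is then:

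| Assumed onset | Assumed duration | Current schedule | With Day 56 |
|---|---|---|---|
| Day 8–22 | 14 days or more | 0% | 0% |
| Day 8–36 | 14 days | 50% | 50% |
| Day 8–36 | 28 days | 50% | 21% |
| Day 15–45 | 28 days | 77% | 20% |
| Day 15–45 | 60 days | 27% | 0% |
| just after Day 22–60 | 28 days | 100% | 26% |

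Example, third row: onset from Day 8 to Day 22 is caught on Day 22, which is 14/28, so 50% is missed. With Day 56, onset from Day 28 to Day 36 is also caught, leaving Day 22 to Day 28, or 6/28 = 21%. Every assumed onset is Day 8 or later, so the Day 2 sample detects nothing in any row and dropping it changes no figure. The current-schedule column runs from 0% to 100%, depending wholly on assumptions that the documents cannot settle.

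**The case against.** The strongest reply is that the schedule is internally consistent, ADA is one of several secondary markers summarised descriptively, and coverage is better than it first looks. Much of that stands. Nothing contradicts anything else, and the primary endpoints are untouched. Table 1 marks the DM199 panel with an unbracketed X at early withdrawal, and footnote 12 restricts only bracketed items to Days 1–22. A subject who withdraws during follow-up is therefore due a sample inside the gap, which is why the point is confined to completers. That Day 2 is uninformative for a new antibody is a general expectation, not something the documents state.

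Several stronger readings are tempting and are not supported:

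- *Any transient response would be missed.* No. A response present on Day 22 is caught. The 68 of 90 days (75.6%) is calendar time, not a probability of missing a response.
- *A negative result would add little to the 28-day finding.* No. Day 90 is 90 − 28 = 62 days later, and the population (acute stroke) and the IV-then-SC regimen are both new. The earlier 28-day diabetes study had "DM199 administered subcutaneously for 28 days", and Section 1.1 does not say how many subjects its antibody statement covers.
- *Adverse events around Day 56 could not be related to antibody status.* No. Section 6.3.3 allows additional laboratory tests in following up an event, and the Day 22 and Day 90 results bracket it.
- *The fall in monkey exposure on repeat dosing in Section 1.2 points to antibodies.* That section makes no such link. A response that early would in any case bear on the period before Day 22, not after it.
- *ADA would be reported as a mean change.* Section 8.3 already provides counts and percentages for categorical variables, and Section 8.3.5 applies change from baseline only as applicable.

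**Conclusion.** The concern holds in a limited form. For completers, about 30 of them on DM199, an ADA response that starts after the Day 22 draw and ends before Day 90 cannot be seen on the current schedule. The gap is 68 days (66 to 70 with the visit window). The Day 2 sample offers little in exchange, assuming that a newly induced antibody does not form within about a day. How many responses would be lost cannot be stated, because the documents give no onset, duration or rate.

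This is a limitation of the design and not an error or a contradiction. It is worth correcting because the means are already in the visit schedule. The correction reduces the gap without closing it: a response lasting less than about 34 days can still fall between draws.

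**What to change.** Give ADA its own schedule of baseline, Day 22 (pre-dose), Day 56 and Day 90, in place of Day 2. Change the synopsis, Sections 2.2.2 and 8.2.2, Table 1 with footnote 8, and Section 5.9.2. In footnote 8 and Section 5.9.2, separate ADA from the plasma concentration of DM199 and the other PD markers, which stay at baseline and Days 2, 22 and 90. Take the Day 56 ADA sample from the existing clinical laboratory draw.

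Cost: a protocol amendment, a Central Laboratory Manual update (the manual was not available, so tube and handling needs should be confirmed against it) and loss of the Day 2 ADA value. The number of ADA samples per subject stays at four, with no new visit or venepuncture. The interval before the first post-baseline ADA result becomes about 21 days.
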